4.0 ANALYSIS SETS

4.1 Intent-to-Treat (ITT) Analysis Set

The intent-to-treat (ITT) analysis set will include all patients who are randomized, with study drug assignment designated according to initial randomization, regardless of whether or not patients receive the study drug to which they were randomized. The primary efficacy analysis will be based on the ITT analysis set.

4.2 Modified Intent-to-Treat (mITT) Analysis Set

The modified intent-to-treat (mITT) analysis set will include ITT patients with Western Blot immune response data at Baseline (prior to treatment) and at Week 10 in Part A. Due to inherent assay challenges with the Elispot assay, the extent and availability of the Elispot data lagged behind the complete set of Western Blot data available for analysis. Western Blot data will be unblinded and used to support the immune response evaluation of the dose levels of seviroptimut-L. All Elispot data will be provided when available.

4.3 Safety Analysis Set

The safety analysis (SA) set consists of all patients who receive at least 1 dose of study drug with treatment assignments designated according to actual study treatment received. This will be the primary population for evaluating treatment administration/compliance and safety.

4.4 Adequately Treated Analysis Set (ATAS)

The adequately treated analysis set (ATAS) will include all patients according to study intervention actually received, require at least 50% of intended injections of study intervention, and who have no major protocol violations. The ATAS analysis will be supportive of the primary analyses based on the ITT analysis set.

4.5 Treatment Misallocations

The following rules will be used for patients who were allocated to the wrong treatment group:

- If patients were *randomized but not treated*, then they will be reported under their randomized treatment group (ITT) for efficacy analyses. However, they are by definition excluded from all safety analyses.
- If patients were *randomized but took incorrect treatment*, then they will be reported under their randomized treatment group (ITT) for all efficacy analyses, but will be reported under the treatment they actually received for all safety analyses.
- For analyses presenting the ATAS set, all patients will be presented under the treatment they actually received.

4.6 Handling of Dropouts or Missing Data

In general there will be no imputation of missing data, other than for partial dates, in the analysis of the primary and secondary endpoints. Imputation in other analyses will depend on the purpose of the analysis and will be described as appropriate, specifically with regards to the analysis of adverse events. Variations of analysis without imputation will be done as sensitivity analyses and as appropriate.

The data items associated with the key analyses are not generally susceptible to being missing, but there are special considerations for dates of events. The following imputation rules will be applied to missing date elements only for dates of events used in the analysis of primary and secondary endpoints:

- Dates with missing day of the month will be completed by imputing the missing day of the month as the 15th day of that month, provided another date to be used in the computation of an interval is not in the same month. If the day of the month is missing and the other date is in the same month, then the missing day of the month will be taken as half the distance to the beginning or end of the month (depending on expected sequence). If both dates to be used in the computation of an interval are missing day of the month then an interval of 15 days (plus or minus) will be used.
- Dates with both month and day of month missing will be imputed as July 1 of the known year provided another date in the same year is to be used in the computation of an interval. If both the month and day of the month are missing and another date in the same year is to be used in the computation of an interval, then the missing date components will be taken as the half the distance from the other date until the beginning or end of the year (depending on expected sequence). If both dates to be used in the computation of an interval are missing both month and day of the month then an interval of 180 days (plus or minus) will be used.
- Dates missing the year or all three components (day, month, and the year) will not be imputed.

Key analyses may depend on the date of the first occurrence of an event associated with the endpoint. When the event has yet to occur the analysis will nonetheless require an analytical date be available for the analysis. These are known as censored or truncated dates. A censored date is the date of the most recent assessment for the event for a patient for which the event of interest has yet to occur and for which additional time may lead to observation of the event of interest. A truncated date is the date of a

competing event that precludes the observation of the event of interest. The distinction between designating an analytical date as censored or truncated will depend on the purpose of the analysis and will be designated for each analysis. For example, if death is the event of interest and a patient is still alive and being followed for the date of death then the date last known alive is a censored date, whereas the date a patient withdraws consent for continued follow-up of vital status (a competing event) is a truncated date. Please note that the nature of the competing event will dictate whether the competing event is permanent. For example, the date of death for a patient who has withdrawn consent may later become known passively from governmental death records.

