5.2.10 Survival Monitoring of Subjects after Recurrence

Subjects with confirmed recurrent disease (see Section 9.3) (and who are not continuing to receive study drug per section 7.2.4) will no longer attend study visits, but will be monitored for survival at least every 6 months (+/- 14 days) through telephone contact until the study is terminated/completed or the subject is withdrawn or lost to follow-up. At the telephone contact, the subject will be asked for information on any additional cancer therapy he/she has started. Contact in-person is acceptable in lieu of a telephone contact. Survival of subjects lost to follow-up by telephone will be tracked by the investigator through the Social Security Death Index in the US, or other similar database outside the US if available.

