6.9 Parts B1 and B2 Efficacy Endpoints

6.9.1 Overall Survival (OS)

The survival analysis objective is to ascertain whether the survival time distribution for patients randomized to the experimental arm is consistent with longer survival as compared to patients randomized to the control arm. All randomized patients will be included in the primary survival analysis in Part B2 or the descriptive secondary analysis of survival in Part B1 according to the randomized arm (intent-to-treat).

The following dataset variables (actual variable names may be different in the analysis datasets) are to be derived from the study database associated with a data cutoff date and used to perform the analysis of survival associated with that data cutoff:

| Variable Name | Label | Definition |
|---------------|----------------------------|---|
| strat | Randomization Stratum | A variable having a unique value for each possible combination of factors used in the stratified randomization scheme. |
| randd | Date of Randomization | Date patient is randomized. |
| expi | Experimental Arm Indicator | expi = 1 if patient is randomized to the experimental arm. expi = 0 if patient is randomized to the control arm. |
| di | Death Indicator | 
• di = 1: The patient is known to be dead. The value of dd (see below) is the date of death.• di = 0: The patient is not known to be dead and is not known to have had a competing event. The value of dd is the date the patient is last known to be alive for a patient that has yet to experience either death or a competing event (see below). di = 0 indicates that dd is a censored date. |

| | | |
|-----------|---------------|--|
| | | 
• di = -1: The value of dd is the date the patient was classified as having a competing event. di = -1 indicates that dd is the date of a competing event. |
| dd | Date of Death | The date of death (di = 1) or the date last known to be alive (di = 0) or the date of competing event (di = -1). See data imputation rules previously specified. |
| dt | Time to Death | dt = dd - randd |

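### SAP 4.6 gives no date to a known death of unknown year, and completes other partial dates without bounding them by the last contact alive; the effect is probably small and the repair is one paragraph

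*SAP*

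**What the plan says.** SAP 4.6 (Handling of Dropouts or Missing Data) sets these rules for event dates in the primary and secondary analyses:

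- **Year unknown, or nothing known:** "Dates missing the year or all three components (day, month, and the year) will not be imputed".
- **Day unknown:** the date is completed by "imputing the missing day of the month as the 15th day of that month". If the other date of the interval falls in that month, half the distance to the start or end of the month is used instead.
- **Month and day unknown:** the date "will be imputed as July 1 of the known year provided another date in the same year is to be used in the computation". The next sentence prescribes half the distance to the start or end of the year, under the same condition.
- **Both dates incomplete:** if both "are missing day of the month then an interval of 15 days (plus or minus) will be used". The parallel rule, where both lack month and day, is 180 days.

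SAP 6.9.1 defines the survival variables. For the death code, "The patient is known to be dead. The value of dd (see below) is the date of death". For the censored code, "The patient is not known to be dead and is not known to have had a competing event". Survival time is the death date minus the randomisation date; SAP 6.9.2 does the same for recurrence-free survival (RFS). SAP 6.9.1 adds: "All randomized patients will be included in the primary survival analysis in Part B2". Addendum 1 makes the Full Analysis Set primary and takes the randomisation date from the IVRS. It does not amend 4.6.

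Protocol 5.2.10 says that patients after recurrence "will be monitored for survival at least every 6 months (+/- 14 days) through telephone contact". Those lost to telephone follow-up are traced through the US death index, or a similar database elsewhere if one is available.

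**The concern.** A site may learn that a patient has died without learning when. Under 6.9.1 that patient takes the death code, but 4.6 leaves the death date empty, so the survival time is missing. The LIFETEST and PHREG steps printed in the SAP leave out a record with no time. Recoding the patient as censored would contradict the definition of that code and would still lose the death. Either way an event is lost because it occurred, although follow-up usually brackets it. This departs from the stated analysis set. Moving to the Full Analysis Set does not help, because it removes only patients who never started study treatment. The planned analyses without imputation cannot restore the event either. Nor does the SAP say whether such a death counts toward the 432 that trigger the final Part B2 survival analysis.

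The second issue is ordering. For an overall survival (OS) or RFS event, the other date of the interval is randomisation. The SAP's appeal to expected sequence therefore orders the event against randomisation only, and nothing keeps it after the last contact alive.

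The stake is bias if undated deaths differ between arms, and case-by-case dating of deaths if the gap is found late.

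**Working it through.** **1. Where an undated death goes.** Death code: needs a date. Censored code: only if not known dead. Competing-event code: definite loss to follow-up or withdrawal of consent. None fits a known death without a year.

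**2. Imputed date before a live contact: examples.**
- Alive on 20 Oct 2018, died in Oct 2018, day unknown, randomised in another month: imputed 15 Oct, 5 days before the contact.
- Alive on 1 Oct 2018, died in 2018, month unknown: July 1 is 3 months before the contact.

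**3. How often.** Assume the death is uniform over the year and the last contact precedes it by a uniform 0–6 months.
- Day missing: the 15th lies about 14.5/30.4 = 0.477 of the way through the month. Probability = (1 − 0.477)² / (2 × 6) = 0.274/12 = 0.023.
- Month and day missing: July 1 is month 6. Probability = (1/12) × ∫ from 6 to 12 of (u − 6)/6 du = (1/12) × 3 = 0.25.
- A simulation of 2,000,000 draws gave 2.3% and 25%. With 3-month gaps it gave 4.6% and 37%, and with 1-month gaps 13.7% and 46%.

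The month-and-day figures apply July 1 to every year-only death, which is not what the text says (step 4).

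**4. The July 1 condition.** As printed, July 1 and the half-distance rule both apply when another date in the same year is used. Such a date has two conflicting rules, and a year-only date with no other date in that year has none. A negative appears to be missing from the first condition.

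**5. Random loss of events.** The SAP's Part B1 design was simulated with its stage rates and shares, its 1- and 3-month delay parameters, 325 patients at 2:1 and 126 events. Power was 80.1% at the SAP's simulated alpha of 0.0887, against 80.5% stated. For Part B2 RFS it was 90.4% at alpha 0.0126, against 90.2% stated. At nominal alpha, with 1%, 2%, 5% or 10% of events undated at random:

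| Analysis | None lost | 1–10% lost |
|---|---|---|
| B1 RFS, patients excluded | 82.5% | 80.2–81.9% |
| B1 RFS, patients censored | 82.5% | 80.4–81.5% |
| B2 RFS, patients excluded | 93.1% | 91.5–93.5% |
| B2 OS, Schoenfeld, one-sided 0.005, no delay | 94.9% | 94.7% falling to 92.2% |

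The simulation standard error is about 0.6 points, so the RFS cost is about 0–2 points.

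**6. One-sided loss in Part B2 OS.** The plan's own figure first: one-sided 0.002625 gives z = 2.79, and exp(−2 × 2.79/√432) = 0.764, the SAP's critical hazard ratio. Now assume 1–2% of 432 deaths undated: 4.3–8.6, say 4–9, all in one arm.
- If the patient stays at risk and is censored, each death moves z by 0.5/√(432/4) = 0.048: 0.19 for 4 deaths, 0.43 for 9.
- If the patient is dropped, the time at risk goes too. With 432/800 = 54% dead and exponential times, the cumulative hazard at the end is −ln 0.46 = 0.777. Its mean at death is (1 − 1.777 × 0.46)/0.54 = 0.34. Each death then moves z by (1 − 0.34) × 0.048 = 0.032: 0.13 for 4, 0.29 for 9. Simulation of 800 patients and 432 deaths gave about 0.13–0.30.
- On the log hazard ratio scale, 0.13–0.30 times 2/√432 = 0.096 is 0.013–0.029, or 1–3% of the hazard ratio.
- If each death is equally likely to fall in either arm, all on one side has probability 2 × 0.5⁴ = 12.5% for 4 deaths and 2 × 0.5⁹ = 0.4% for 9.

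**The case against.** The SAP says that the key data items are not generally prone to being missing, and both documents point to death records as a source. No undated death is reported, and the 1–2% is an assumption. The trial is double-blind, so a large imbalance between arms is unlikely. Part B2 is conditional on Part B1, where survival is descriptive. All of this stands, and it limits the size. It does not supply a rule for the patient who falls in the gap.

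Three stronger readings are tempting and should not be drawn:

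- **That recurrences are lost in the same way.** Addendum 1 dates a recurrence from the first confirmation, brain MRI or biopsy finding, each with its own date. A patient with a dated recurrence is already an RFS event, whatever happens to the death date. The exposure is mainly deaths.
- **That the 15- and 180-day intervals distort the primary endpoints.** Primary OS and RFS start at the IVRS randomisation date, so both dates are not incomplete together. The rule can matter only between two clinical dates, as in the Addendum's sensitivity analysis with a 120-day window. Read literally, an assessment in March 2017 and a death in November 2017 would be 15 days apart, rather than the 245 between the two mid-months. The sentence follows the same-month case, so a narrower meaning may be intended.
- **That the survival z would move by 0.19–0.43.** That is the effect of censoring the deaths while keeping the patients at risk. For dropping them it is 0.13–0.30, and both need every loss in one arm.

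**Conclusion.** The gap is real, and it lies in a stated rule rather than in missing detail. A known death of unknown year falls out of OS, and out of RFS if no earlier recurrence was dated. A partially dated death can be placed before a documented live contact. A year-only date with no other date in that year has no valid rule as printed.

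The effect is probably small. The 2% and 25% rest on uniform dates and six-monthly contacts, and the 25% also on applying July 1. The 1–10% loss and the 4–9 deaths are assumptions, because the documents give no rate. Even the extreme one-arm case moves the Part B2 survival z by only 0.13–0.30. The documents do not show that any event has been misdated, or that a result would change. The change is worth making because it is cheap and removes a judgement that should not be made after unblinding.

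**What to change.** Amend SAP 4.6 before the analysis concerned is unblinded:

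1. Impute an incomplete or missing date of a known death, or other known event, as the midpoint between two limits. The lower limit is the latest of randomisation, the last date documented event-free, and the start of the known month or year. The upper limit is the earliest of the contact or record at which the event was learned (where recorded), the end of the known month or year, and the data cutoff.
2. Correct the July 1 condition, if that rule is kept anywhere, so that it applies when no other date in the same year is used.
3. Limit the 15- and 180-day intervals to two dates in the same month or the same year; otherwise compute the interval from the completed dates.
4. Keep the analysis without imputation as sensitivity.

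The cost is one SAP paragraph and a small programming change; no alpha level or event target changes. The documents do not show a field for the date on which a death was first reported. Where none exists, the upper limit falls back on the end of the known period or the cutoff. The downside is a few imputed dates that would now be left missing, with wide brackets for patients lost to follow-up.

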5.0 STATISTICAL CONSIDERATIONS

5.1 Part A

The size of Part A (33 patients per arm) was computed based on having no greater than a one-sided 20% likelihood of a false positive conclusion for the immune response statistical criterion. See the subsequent section [6.8.1 “Part A Immunological Statistical Success”](#) for the statistical operating characteristics of the Part A statistical analysis.

Recruitment will continue in Part A until the analysis of Week 10 data has been completed on the first 99 randomized subjects. This will result in an “over enrollment” for Part A to avoid a discontinuation of recruitment and ensure a complete data set for Part A evaluation.

Patients assigned to the Placebo arm during Part A accrual will be offered the option of receiving 40 µg seviprotimut-L selected from Part A under an Open-Label Extension protocol. Patients assigned to the Part A active arms will remain on the dose assigned and be followed until the end of the study. All Part A patients will be separately tabulated and used in the assessment of safety. They may also be used in exploratory efficacy analyses, but will not be part of the primary or secondary Part B evaluations.

5.2 Part B

The decision regarding initiation of Part B of the study was to be based solely on biomarker and safety data from Part A, specifically not including clinical outcome data. Part A patients are not included in the primary analyses of Part B data. This revision to the SAP describes revisions to Part B leading to Part B1, an analysis of RFS, conditionally followed by Part B2, a follow-on definitive phase of the trial.

The description of the methods of analysis that follow are for all parts as applicable relative to the endpoints unless otherwise specified. Depending on the study Part an analysis may be descriptive (exploratory) or formal depending on study Part.

5.2.1 Part B1

Part B1 is a two-arm comparison of the efficacy of the experimental arm where the intended intervention is the experimental vaccine (Arm V) against a control arm where the intended intervention is placebo (Arm P). The primary analysis is based on recurrence-free survival (RFS). This analysis is based on the original hypothesized RFS hazard ratio and assumed control arm RFS distribution. The analysis is specified to be an intent-to-treat comparison of Arm V to Arm P using the stratified logrank

test. The major change brought about as a result of splitting the original Part B into Parts B1 and B2 is to implement a relaxed the type I error probability for Part B1.

The following table is used to specify Arm P (control arm) reference data by stage strata. The original specification of proportions expected came from a review of the articles reporting outcome from recent trials in melanoma. The empirical proportions come from trial experience to date. The stratum-specific empirical proportions are used to compute the trial size and timing as described subsequently.

| Stage | Original Proportions (%) | Empirical Proportions (%) | RFS median (y) | RFS rate |
|--------|--------------------------|---------------------------|----------------|----------|
| II | 30 | 30.9 | 4.5 | 0.154 |
| IIIA | 36 | 30.4 | 3.5 | 0.198 |
| IIIB/C | 34 | 38.7 | 1.7 | 0.409 |

The best single source of effect size data is reference (1). This article reports data from a small (38 patient) double-blind randomized trial of a similar vaccine. The estimated medians for RFS are 0.6 and 1.6 years for placebo and vaccine, respectively, providing a crude hazard ratio estimate of 0.38 ($= 0.6/1.6$). Therefore, Polynoma's hypothesized RFS hazard ratio is 0.625 for RFS, corresponding to a 37.5% smaller RFS hazard rate for Arm V patients. This hypothesized hazard ratio is consistent with a clinically meaningful effect, especially when weighed against the expected low adverse event profile.

There is evidence, both from melanoma trials and trials of therapeutic vaccines in other diseases, that there may be a delay in the effect of an experimental vaccine. Taking into account the possibility of a delay in effect precludes using trial size computation methods that assume proportional hazards because the proportional hazards assumption is no longer valid. Thus, some method other than the standard formulas for computing the required number of events must be used. For this trial simulations were used for delayed effect scenarios. An appendix to this document describes the simulation methodology.

For RFS analysis scenarios with delayed effect, the delay of effect is parameterized as follows: The RFS hazard ratio is assumed to be one until 1 month, followed by a period of 3 months over which the hazard ratio linearly decreases from one to 0.625, followed by a hazard ratio of 0.625 from 4 months forward.

The first year (January 2015 through December 2015) accrual experience in this study was 212 patients. The Part B1 RFS analysis being described is based on a total accrual of 325 patients which is projected to occur in June 2016.

This RFS analysis is based on one-sided alpha of 0.10 (equivalent to two-sided 0.20 for planning purposes) and statistical power of 80%. No interim analyses are planned for this RFS analysis.

Simulations with 10,000 replications based on the accrual of 325 patients as described above and the above specified alpha and power requires 126 RFS events and the last of these events is projected to occur 3.21 years following the start of accrual, that is, March 2018. The simulation estimate of alpha is

0.0887, the simulation estimate of power is 80.5%, and the critical RFS hazard ratio is estimated to be 0.792, corresponding roughly to a 26% longer median.

Overall survival for subjects in Part B1 will be followed and reported as a descriptive endpoint to the IND, as appropriate. Survival in Part B1 will be assessed as a safety outcome at the time of the final Part B1 RFS analysis. Patients enrolled in Part B1 will be followed for survival and have their vital status systematically assessed following the Part B1 RFS analysis in order to descriptively assess the long-term survival experience of Part B1 patients. The survival data from Part B1 will not be pooled with survival data from Part B2 for the formal survival analysis of Part B2.

The original trial was planned based on accruing 960 patients in only 2 years. The above computations for Part B1 are based on accruing 325 patients in 1.5 years, a rate less than half (45%) of the originally assumed accrual rate. The original final RFS analysis was projected for 3.8 years based on the overly optimistic assumed accrual rate, or October 2018. The Part B1 analysis with a relaxed alpha of 1-sided 0.10 provides an RFS assessment at about the same time as originally projected.

